2.7.3 Handling of missing values/censoring/discontinuations

Patients with unknown angiomyolipoma response status will be treated as non-responders in the calculation of the angiomyolipoma response rate in the Full Analysis Set at the end of the trial.

If an AML progression is documented after two or more missing assessments or non-adequate assessments, then the date of AML progression will be censored at the date of the last adequate assessment. If an AML response is observed after a single missing or non-adequate assessment, the actual date of event will be used.

TTAP will be censored if angiomyolipoma progression is not observed before the first to occur out of (i) the cut-off date for the analysis, or (ii) the date when a further systemic anti-angiomyolipoma medication is started, (iii) the date of a angiomyolipoma-related surgery or (iv) the date of death. The censoring date will be the date of the most recent MRI assessment before the first of any of these four events occurred.

Time to angiomyolipoma response applies only to patients who achieve an angiomyolipoma response, i.e., patients in the analysis will have known times to angiomyolipoma response and there will be no censored times.

Duration of angiomyolipoma response will be censored if angiomyolipoma progression is not observed before the first to occur out of (i) the cut-off date for the analysis, or (ii) the date when a further systemic anti-angiomyolipoma medication is started, (iii) the date of a angiomyolipoma-related surgery or (iv) the date of death. The censoring date will be the date of the most recent MRI assessment before the first of any of these four events occurred.

Other missing data will simply be noted as missing on appropriate tables/listings.

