All patients will have a CT/MRI of the kidney performed at 12, 24 and 48 weeks in the open-label treatment phase, after the start of study treatment, until angiomyolipoma progression. A CT/MRI of the kidneys should be repeated at the End of Treatment (EOT) visit if the patient has discontinued for any reason other than angiomyolipoma progression, and if it has been more than 8 weeks since their most recent kidney CT/MRI.

In addition to the CT/MRI of the kidney, patients with a SEGA lesion having a longest diameter ≥ 1.0 cm documented at screening will also have a MRI/CT of the brain at 12, 24 and 48 weeks in the open-label treatment phase. For each patient, the same imaging modality should be used throughout the study. All kidney CT/MRIs and brain MRI/CTs will be sent to the central radiologist for an independent centralized radiology review. The central radiologist will determine the angiomyolipoma volume and verify whether the radiological criteria for angiomyolipoma response have been met ([Section 7.2.1.1](#)). Since not all study centers will have the technical capability to measure angiomyolipoma volume, there is no plan to collect data from the local radiologist at each site. MRI and CT scans must be digitized and sent to Central Radiology within 2 business days of the scan date. The central review of the CT/MRIs will be conducted at the agreed upon frequency between Novartis and the assigned Imaging

Vendor after its receipt by the central radiology vendor. Once the data is available, the results will be sent immediately to the study site and to Novartis. Clinical suspicion of angiomyolipoma progression at any time requires a physical examination and expedited radiological confirmation by the Independent Central Radiology Reviewer.

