8.1 Adverse events

8.1.1 Definitions and reporting

An adverse event is defined as the appearance of (or worsening of any pre-existing) undesirable sign(s), symptom(s), or medical condition(s) that occur after patient's signed informed consent has been obtained.

Abnormal laboratory values or test results occurring after informed consent constitute adverse events only if they induce clinical signs or symptoms, are considered clinically significant, require therapy (e.g., hematologic abnormality that requires transfusion or hematological stem cell support), or require changes in study medication(s).

Adverse events that begin or worsen after informed consent should be recorded in the Adverse Events CRF. Conditions that were already present at the time of informed consent should be recorded in the Relevant Medical History page of the patient's CRF. Adverse event monitoring should be continued for at least 30 days following the last dose of study treatment. Adverse events (including lab abnormalities that constitute AEs) should be described using a diagnosis whenever possible, rather than individual underlying signs and symptoms. When a clear diagnosis cannot be identified, each sign or symptom should be reported as a separate Adverse Event.

Adverse events will be assessed and graded according to the Common Terminology Criteria for Adverse Events (CTCAE) version 4.03. Grade 1 to 5 will be used to characterize the severity of the Adverse Event.

If CTCAE grading does not exist for an adverse event, the severity of mild, moderate, severe, and life-threatening, death related to the AE corresponding respectively to Grades 1 - 5, will be used. Information about any deaths (related to an Adverse Event or not) will also be collected through a Death form.

The occurrence of adverse events should be sought by non-directive questioning of the patient (subject) during the screening process after signing informed consent and at each visit during the study. Adverse events also may be detected when they are volunteered by the patient (subject) during the screening process or between visits, or through physical examination, laboratory test, or other assessments. As far as possible, each adverse event should be evaluated to determine:

1. The severity grade (CTCAE Grade 1-5)
2. Its duration (start and end dates or ongoing at end of study)
3. Its relationship to the study treatment (reasonable possibility that AE is related: No, Yes)

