2.7.1 Secondary endpoints

The efficacy endpoints will be based on the independent central radiology review of CT/MRI assessments of the kidneys to determine the volumes of target lesions in the kidneys.

The efficacy analysis will be performed using the FAS.

Definition

Each post baseline CT/MRI assessment of the kidneys will be classified by the Independent Central Radiology Review as either angiomyolipoma response, stable disease, angiomyolipoma progression or not evaluable, based on the combined radiological assessments of target angiomyolipoma volume, kidney volumes and new angiomyolipoma lesions.

An overall angiomyolipoma response will then be calculated by Novartis combining the angiomyolipoma radiological assessment as provided by the Independent Central Radiology Review and angiomyolipoma-related bleeding reported by the investigator on the Adverse

Events CRF page. Clinical review is required in order to identify all occurrences of angiomyolipoma-related bleeding reported by the investigators.

Angiomyolipoma response is defined as:

- A reduction in angiomyolipoma volume of at least 50% relative to screening, where angiomyolipoma volume is the sum of the volumes of all target angiomyolipomata identified at screening.

In addition, angiomyolipoma response requires satisfying all of the following criteria:

- No new angiomyolipomata ≥ 1.0 cm in longest diameter are identified
- Neither kidney increases in volume by more than 20% from nadir (where nadir is the lowest kidney volume obtained for the patient, separately for each kidney, previously in the trial including baseline)
- The patient does not have any angiomyolipoma-related bleeding of grade ≥ 2 (as defined by NCI Common Terminology Criteria for Adverse Events (CTCAE), version 4.03).

Angiomyolipoma progression is defined as one or more of the following:

- An increase from nadir of 25% or more in angiomyolipoma volume to a value greater than screening, where angiomyolipoma volume is the sum of the volumes of all target angiomyolipomata identified at baseline and where nadir is the lowest angiomyolipoma volume achieved by the patient previously in the trial (including screening)
- The appearance of a new angiomyolipoma ≥ 1.0 cm in longest diameter
- An increase from nadir of 20% or more in the volume of either kidney to a value greater than screening, where nadir is the lowest kidney volume obtained for the patient, separately for each kidney, previously in the trial (including screening)

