- Angiomyolipoma-related bleeding grade ≥ 2 as defined by NCI CTCAE, version 4.03.

Stable disease (SD): insufficient shrinkage in angiomyolipoma volume to qualify for response and the absence of progression.

Not evaluable (NE): CT/MRI performed but not readable (e.g., not all designated target lesions are included in a follow up image due to technical error).

The **best overall angiomyolipoma response** is the best response recorded from treatment until the first to occur out of (i) angiomyolipoma progression, (ii) the cut-off date for the final analysis, (iii) the date when a further systemic anti-angiomyolipoma medication is started, (iv) the date of an angiomyolipoma-related surgery, or (v) the date of death.

Angiomyolipoma response rate

Angiomyolipoma response rate, is defined as the proportion of patients with best overall angiomyolipoma response status of “angiomyolipoma response” (as defined as above) during maximum treatment duration of 48 weeks using data from the Independent Central Radiology Review of CT/MRIs and the Adverse Events CRF page (to identify angiomyolipoma-related bleeding of grade 2 or worse as defined by NCI CTCAE version 4.03). Angiomyolipoma response rate will be calculated based on the FAS and presented together with an exact 95% confidence interval for all patients.

Overall angiomyolipoma response (either angiomyolipoma response, stable disease, angiomyolipoma progression or not evaluable) at each assessment will be summarised by frequency and percentage.

Supportive analyses will include descriptive summaries of the sum of the volumes of target angiomyolipoma lesions from both kidneys (mean, standard deviation, 25th and 75th percentiles, median, minimum and maximum) at each assessment, using the time windows defined in [Section 2.1.1.7](#). Change from baseline (actual and percentage) in the sum of volumes of target angiomyolipoma lesions will also both be summarized descriptively at each assessment.

A waterfall plot will present the best percentage change from baseline in target angiomyolipoma volume at each assessment.

Note that patients with best overall angiomyolipoma response of Not Evaluable will be treated as non-responders in the calculation of the best overall angiomyolipoma response rate in the FAS, but will be excluded from the denominator for the waterfall plots.

Angiomyolipoma progression

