Angiomyolipoma progression, is defined as the proportion of patients with an angiomyolipoma progression during maximum treatment duration of 48 weeks, as defined as above, using data from the Independent Central Radiology Review of CT/MRIs and the Adverse Events CRF page (to identify angiomyolipoma-related bleeding of grade 2 or worse as defined by NCI CTCAE version 4.03).

Angiomyolipoma progression rate will be calculated based on the FAS and presented together with an exact 95% confidence interval for all patients.

Time to angiomyolipoma progression

Time to angiomyolipoma progression (TTAP) is defined as the time from the start date of everolimus to the date of the first documented angiomyolipoma progression, where angiomyolipoma progression is defined as above. TTAP will be censored if angiomyolipoma progression is not observed before the first to occur out of

- (i) the cut-off date for the analysis, or
- (ii) the date when a further systemic anti-angiomyolipoma medication is started, or
- (iii) the date of a angiomyolipoma-related surgery or
- (iv) the date of death.

The censoring date will be the date of the last adequate CT/MRI assessment occurring before the first of any of these four events to have occurred, or treatment day 1 if there were no adequate CT/MRI assessments performed post-baseline.

TTAP will be presented in months and is calculated as:

$$(\text{Date of angiomyolipoma progression/censoring} - \text{Start date of everolimus} + 1) \times 12 \div 365.25.$$

The TTAP distribution will be presented descriptively in the FAS using a Kaplan-Meier curve. Summary statistics from the Kaplan-Meier distribution will be determined, including the

median TTAP and the proportions of patients remaining progression-free at 3, 6, and 12 months. These statistics will be given as point estimates with 95% confidence intervals.

Per protocol, tumor assessment was done at Week 4, 12, 24 and 48. At database lock, it was observed that most patients were censored at treatment completion at the time of their Week 48 assessment, and only 3 out of the 40 patients had angiomyolipoma progression observed. 9 patients were discovered to have TTAP greater than the maximum treatment duration of 48 weeks + 7 day window, among which one patient had progressed; this patient had the longest TTAP in the analysis set.

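### The censoring rule for two missed scans also covers AML bleeding, so TTAP can censor a bleed that was observed and dated

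*SAP*

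**What the plan says.** The rule stands in SAP 2.7.3: "If an AML progression is documented after two or more missing assessments or non-adequate assessments, then the date of AML progression will be censored", using the last adequate assessment. It exempts no type of progression.

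SAP 2.7.1 makes progression a composite: "Angiomyolipoma progression is defined as one or more of the following". Three of the four criteria are read from scans (target lesion volume, new lesions, kidney volume). The fourth is "Angiomyolipoma-related bleeding grade ≥ 2 as defined by NCI CTCAE, version 4.03". The Adverse Events CRF is used "to identify angiomyolipoma-related bleeding of grade 2 or worse as defined by NCI CTCAE version 4.03". For each adverse event, Protocol 8.1.1 asks for, among other items, "Its duration (start and end dates or ongoing at end of study".

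TTAP runs from the start of everolimus to "the date of the first documented angiomyolipoma progression, where angiomyolipoma progression is defined as above", so a bleed is a TTAP event. Duration of response ends on the same composite. When TTAP is censored, SAP 2.7.1 uses the last adequate scan, "or treatment day 1 if there were no adequate CT/MRI assessments performed post-baseline".

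Protocol 4.1 sets the imaging schedule: "All patients will have a CT/MRI of the kidney performed at 12, 24 and 48 weeks in the open-label treatment phase". SAP 2.1.1.7 uses the same three time points. The TTAP text in SAP 2.7.1 also mentions a Week 4 tumour assessment, which appears in neither place; I use 12, 24 and 48.

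The progression rate in SAP 2.7.1 is a separate result: the proportion of the FAS with progression within the 48-week maximum treatment duration. Protocol 10.5.2 also calls for a listing and narratives of patients with progression.

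**The concern.** A rule of this kind deals with one problem. When scans are missing, a progression first seen on a later scan could have happened at any time in the gap. A bleed reported as an adverse event does not have that problem, because its occurrence and onset are recorded whether or not a scan was done. As written, the rule lets missing images turn an observed event into a censored observation.

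That censoring is informative, since the patient is censored because a progression was documented. It also discards follow-up during which the patient was observed. The progression rate does not depend on an event date, and nothing in the SAP removes the bleed from it. The same patient could therefore be progressed in the rate and progression-free, then censored, in the Kaplan-Meier curve.

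**Working it through.** **When the rule reaches a bleed.** Both missing or non-adequate scans must come before the bleed. With three scheduled post-baseline scans there are two main paths.

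- *Weeks 12 and 24 missed, bleed between then and Week 48.* With no unscheduled adequate scan there is no adequate post-baseline scan, so TTAP is censored at Day 1. This is the realistic path.
- *Weeks 24 and 48 missed, bleed afterwards.* TTAP is censored at the Week 12 scan, about day 84. Such a bleed comes at about Week 48 or later, so it can also fall outside the 48-week progression rate, and the two results need not disagree.

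**Duration of response.** A responder needs at least one adequate post-baseline scan. If two of the three scheduled scans are missed before the bleed, the bleed is at about Week 48 or later, barring an unscheduled scan. The effect on this endpoint is negligible.

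**Time conversion.** The SAP formula is study day × 12 ÷ 365.25. For the end of the Week 48 window, 343 × 12 ÷ 365.25 = 11.26899 months; the SAP prints this truncated, as 11.268. In the same way, day 1 = 0.03 months, day 84 = 2.76 months and day 200 = 6.57 months.

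**Illustration.** The SAP reports 3 progressions in 40 patients but not all their types and dates, so the dates here are assumed: one radiological progression at day 168, one qualifying bleed at day 200 after missed Week 12 and Week 24 scans, one progression after day 343, and everyone else censored at Week 48 or later. Estimates are Kaplan-Meier with log-log 95% intervals, read just before Week 48.

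- Rule as written: the bleeding patient leaves at Day 1, so 39 are at risk at day 168. Progression-free = 38/39 = 97.4% (83.2 to 99.6).
- Bleed counted on its onset date: (39/40) × (38/39) = 38/40 = 95.0% (81.5 to 98.7).
- The estimated event probability goes from 2.6% to 5.0%.

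**Range.** With no other censoring before Week 48, the bleed's exact date between Week 24 and Week 48 does not change these values. The number of other progressions before Week 48 changes them as follows.

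| Other progressions before Week 48 | Rule as written | Bleed counted |
|---|---|---|
| 0 | 39/39 = 100% | 39/40 = 97.5% |
| 1 | 38/39 = 97.4% | 38/40 = 95.0% |
| 2 | 37/39 = 94.9% | 37/40 = 92.5% |

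The gap is about 2.4 to 2.5 percentage points each time, and from the bleed date on the rule gives the more favourable figure.

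**Scale of one event as a proportion.** 3/40 = 7.5% (exact 95% CI 1.6 to 20.4) against 2/40 = 5.0% (0.6 to 16.9).

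**The case against.** The best counter-argument is that TTAP measures the first progression in a composite. If the Week 12 and Week 24 scans are missing, a radiological progression may have preceded the bleed, so the bleed date need not be the first progression date, and one rule for the whole composite is defensible. Part of this stands: counting the bleed may date the event late. But the bleed date is an upper bound on the first progression time. Late dating keeps a known event; the rule discards it, and on the realistic path nearly all of that patient's follow-up as well.

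It can also be said that the rule was meant for imaging only. The TTAP text in SAP 2.7.1 lists four censoring reasons and omits this one, and an adequate assessment there is a CT or MRI. That reading is plausible for what counts as a missed assessment. It does not narrow which progressions are censored, and SAP 2.7.3 contains no such limit. If imaging only was intended, the SAP should say so.

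Two practical objections stand. Adverse event start dates can be partial, in which case SAP 5.1.2 imputes them. And the SAP already describes data at database lock and a TTAP revision made in light of them, so this would be a second change made after data were seen.

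**Conclusion.** The rule is too broad as worded, and the problem is small. It can convert an observed grade 2 or worse AML bleed into a censored TTAP time when both the Week 12 and Week 24 scans are missing or non-adequate and the bleed comes before Week 48. TTAP is descriptive, with no hypothesis test.

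A reader might infer more than the documents support:

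- *That a bleed is deleted whenever two scans are missed.* Scans missed after the bleed do not trigger the rule, and it censors a date. The bleed still prevents a response and stays in the progression rate, the protocol's listing and narratives, and the adverse event outputs, which serve the primary objective.
- *That a quarter or a third of the events are lost.* One such bleed would be 1 of 4 if it came on top of the 3 reported progressions, or 1 of 3 if it were among them. Both are hypothetical. Neither document reports an AML bleed or a patient with two missed scans. The count of 3 stands beside the description of censored patients, so it may already be the number left after censoring. At least one of the three was kept as an event, since the SAP says it takes the curve to zero.

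The actual effect is unknown and may be nil. The shift of about 2.4 to 2.5 points rests on 40 patients, one affected bleed, zero to two other progressions before Week 48 and no other early censoring.

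**What to change.** In SAP 2.7.3, limit the rule for two missed assessments to progression established by CT or MRI. Add that AML-related bleeding of grade 2 or worse is a TTAP event on its adverse event onset date, imputed under SAP 5.1.2 if partial, regardless of earlier missing scans. State also whether the rule applies to the progression rate.

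Because data at database lock are already described, report this as a disclosed correction. Check whether any patient had a qualifying bleed after two missing or non-adequate scans. If none did, one sentence in the study report settles the point. If one did, show TTAP under both the current rule and the corrected one.

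The cost is a sentence or two in the SAP and one check of existing data; no new data are needed. The downside is that a bleed may be dated later than a radiological progression that went undetected.

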2.8 Safety analyses

The assessment of safety will be based mainly on the frequency of adverse events and on the number of laboratory values that fall outside of pre-determined ranges. Other safety data (e.g., vital signs and special tests) will be considered as appropriate.

All safety outputs will use the Safety Set.

The safety summary tables will include only assessments collected no later than 30 days after the date of last administration of everolimus. The safety summary listings will include all assessments, with those collected later than 30 days after date of last everolimus being flagged.

2.8.1 Adverse events

General rules for AE Reporting

AE summaries will include all AEs starting on or after treatment day 1 (i.e., on or after the start date of everolimus) and no later than 30 days after the last day of everolimus. All AEs will be listed. AEs starting prior to treatment day 1 will be identified in the listings with a starting treatment day less than day 1, and AEs starting later than 30 days after the last day of everolimus will be specifically flagged.

AEs will be summarized by presenting the number and percentage of patients having at least one AE, and having at least one AE in each body system/primary system organ class, and for each preferred term using MedDRA coding. A patient with multiple occurrences of an AE will be counted only once in the AE category.

Separate AE summaries will be presented by primary system organ class, preferred term, and maximum common toxicity criteria (CTC) grade. A patient with multiple CTC grades for an AE will be summarized under the maximum CTC grade recorded for the event.

The frequency of CTC grade 3 and 4 AEs will be summarized separately.

Any information collected (e.g., CTC grades, relationship to study drug, action taken) will be listed as appropriate.

AE summaries

The following adverse event summaries will be produced:

- Adverse events, regardless of study drug relationship, by primary system organ class and preferred term
- Adverse events, with suspected relationship to study drug, by primary system organ class and preferred term
- Adverse events, regardless of study drug relationship, by preferred term
- Adverse events, regardless of study drug relationship, by primary system organ class, preferred term and maximum CTC grade
- Adverse events, with suspected study drug relationship, by primary system organ class, preferred term and maximum CTC grade

- CTC grade 3 or 4 adverse events, regardless of study drug relationship, by primary system organ class and preferred term
- CTC grade 3 or 4 adverse events, with suspected study drug relationship, by primary system organ class and preferred term
- Deaths, by primary system organ class and preferred term
- Serious adverse events, regardless of study drug relationship, by primary system organ class and preferred term
- Serious adverse events, with suspected study drug relationship, by primary system organ class and preferred term
- Adverse events leading to study drug discontinuation, regardless of study drug relationship, by preferred term
- Adverse events requiring dose adjustment or study drug interruption, regardless of study drug relationship, by preferred term
- Adverse events requiring additional therapy, regardless of study drug relationship, by preferred term

Adverse events will be presented in alphabetical order for system organ class, and in descending order of frequency for preferred term within each system organ class.

For the legal requirements of ClinicalTrials.gov and EudraCT, two required tables for on treatment emergent AEs which are not SAEs with an incidence greater than and equal to 5% and on treatment emergent SAEs and SAEs suspected to be related to study treatment will be provided by system organ class and preferred term on the safety set.

If for a same patient, several consecutive AEs (irrespective of study treatment causality, seriousness and severity) occurred with the same SOC and PT:

- a single occurrence will be counted if there is ≤ 1 day gap between the end date of the preceding AE and the start date of the consecutive AE
- more than one occurrence will be counted if there is > 1 day gap between the end date of the preceding AE and the start date of the consecutive AE

For occurrence, the presence of at least one SAE/SAE suspected to be related to study treatment/non SAE has to be checked in a block e.g., among AE's in a ≤ 1 day gap block, if at least one SAE is occurring, then one occurrence is calculated for that SAE.

The number of deaths resulting from SAEs suspected to be related to study treatment and SAEs irrespective of study treatment relationship will be provided by SOC and PT.

